5.5.7 Dermatologic Toxicity

Cetuximab-related dermatologic toxicity should be graded according to the criteria outlined in Table 5 below. According to physician judgment, if a patient experiences ≥ grade 3 rash, cetuximab treatment adjustments should be made according to Table 4B above. In patients with mild and moderate skin adverse events, cetuximab should continue without adjustment.

Table 5: Grading of Cetuximab-Related Skin Changes

| | 1 | 2 | 3 | 4 |
|---|---|--|--|--|
| Pruritus* | Mild or localized | Intense or widespread | Intense or widespread and interfering with ADL | - |
| Rash/acneiform* | Papules and/or pustules covering <10% BSA, which may or may not be associated with symptoms of pruritus or tenderness | Papules and/or pustules covering 10-30% BSA, which may or may not be associated with symptoms of pruritus or tenderness; associated with psychosocial impact; limiting instrumental ADLI; Responds promptly to symptomatic treatment | Papules and/or pustules covering > 30% BSA, which may or may not be associated with symptoms of pruritus or tenderness; limiting self-care ADL; associated with local superinfection with oral antibiotics indicated; Prolonged. | Papules and/or pustules covering any % BSA, which may or may not be associated with symptoms of pruritus or tenderness and are associated with extensive superinfection with IV antibiotics indicated; life threatening consequences |
| Paronychia Onset of grade 3 will require dose modification for cetuximab. See Table 4B above. | Nail fold edema or erythema; disruption of the cuticle | Localized intervention indicated; oral intervention indicated (e.g., antibiotic, antifungal, antiviral); nail fold edema or erythema with pain; associated with discharge or nail plate separation; limiting instrumental ADL | Surgical intervention or IV antibiotics indicated; limiting self care ADL | - |

Cetuximab-Related Rash Management

Skin rash, ranging from dry skin and erythema to a pustular eruption is extremely common during cetuximab therapy. Biopsy of the papulopustular rash demonstrates histopathologic suppurative inflammation and not acne vulgaris. Although the initial rash is sterile, superinfection may occur.

Patients developing dermatologic AEs while receiving cetuximab should be monitored for the development of inflammatory or infectious sequelae, and appropriate treatment of these symptoms initiated. Below are suggestions for managing cetuximab-induced rash, adapted from the NCCN Task Force for the Management of Dermatologic Toxicities Associated with EGFR Inhibition in Patients with Cancer.47 In the event of severe rash not responsive to topical treatments or oral antibiotics, dose modification per Table 4B is indicated.

- Moisturizers: Use of topical emollients to prevent and alleviate skin dryness is strongly advised. Examples include Aquaphor Ointment, Cetaphil Cream, Neutrogena Norwegian Formula Hand Cream, and Vaseline Intensive Care Advanced Healing Lotion.
- **Soap:** A mild, neutral pH soap is recommended.
- Antibiotics: Topical clindamycin or erythromycin, or an oral tetracycline family antibiotic
 (e.g. tetracycline, minocycline, doxycycline) should be considered in the case of
 superinfection or suspected superinfection. Oral minocycline, tetracycline or doxycycline
 may be given prophylactically to patients with a history of severe acneiform eruption
 during prior cetuximab therapy.
- **Antihistamines**: Diphenhydramine or hydroxyzine may be helpful to control itching.
- **Topical Steroids**: Topical therapy with a low potency steroid to the face (e.g. hydrocortisone valerate 0.2%) or a mid-potency steroid to the body (e.g. triamcinolone acetonide 0.1%) may be used for management of cetuximab rash.
- **Sunlight**: It is recommended that patients wear sunscreen (at least SPF 40) and hats and limit sun exposure while receiving cetuximab as sunlight can exacerbate any skin reactions that may occur.
- Over-the-counter medications: Over-the-counter acne vulgaris medications (e.g. benzoyl peroxide) are not advised.
- Retinoids: Use is not advised.

5.5.8 Cetuximab Infusion Reaction

A cetuximab infusion reaction will be managed as described in Table 6 below. If there is any question as to whether an observed reaction is an infusion reaction of Grades 1-4, [name] should be contacted immediately to discuss and grade the reaction.

Should an infusion reaction occur, retreatment will be managed as follows: Once a cetuximab infusion rate has been decreased due to an infusion reaction, it will remain decreased for all subsequent infusions. If the subject has a second infusion reaction with the slower infusion rate, the infusion should be stopped, and the subject should receive no further cetuximab treatment. If a subject that experienced an initial cetuximab infusion reaction experiences a Grade 3 or 4 infusion reaction at any time, the subject should receive no further cetuximab treatment.

Table 6: Management of Cetuximab Infusion Reaction

| Grade | Management |
|--|--|
| Grade 1: Transient flushing or rash; drug fever < 38° C (< 100.4° F) | For mild infusion reactions manifesting only as delayed drug fever, consider administering prophylactic antihistamine medications for subsequent doses. Maintain the cetuximab dose but slow the infusion rate by 50%. Acetaminophen or a non-steroidal anti-inflammatory drug (NSAID) may be administered prior to subsequent cetuximab infusions, if not otherwise contraindicated in subjects. |
| Grade 2: Rash; flushing; urticaria; dyspnea; drug fever ≥ 38° C (≥ 100.4° F) | For moderate infusion reactions manifesting only as delayed drug fever, slow the infusion rate for cetuximab by 50%, and consider administration of antihistamine medications and/or steroidal medications. Maintain the cetuximab dose. Acetaminophen or a non-steroidal anti-inflammatory drug (NSAID) may be administered prior to subsequent cetuximab infusions, if not otherwise contraindicated in subjects. |
| Grade 3: Symptomatic bronchospasm with or without urticaria; parenteral medication(s) indicated; allergy- related edema/angioedema; hypotension | Severe infusion reactions requires immediate interruption of cetuximab infusion and permanent discontinuation from further treatment with cetuximab. Appropriate medical therapy including epinephrine, corticosteroids, diphenhydramine, bronchodilators, and oxygen should be available for use in the treatment of such reactions. Subjects should be carefully observed until the complete resolution of all signs and symptoms. |

| Grade 4: | NO FURTHER CETUXIMAB |
|-------------|---|
| Anaphylaxis | Life-threatening infusion reactions require immediate interruption of cetuximab infusion and permanent discontinuation from further treatment with cetuximab. Appropriate medical therapy including |
| | epinephrine, corticosteroids, diphenhydramine, bronchodilators, and oxygen should be available for use in the treatment of such reactions. Subjects should be carefully observed until the complete resolution of all signs and symptoms. |

6. RESPONSE ASSESSMENT

Patients are to be re-evaluated for response every 8 weeks, +/- 7 days during at least Cycle 1 through Cycle 12. Disease assessment is performed per standard of care and per physician's determination of clinical indication.

Consistent with standard of care, subjects who remain on treatment after cycle 12 can be transitioned to re-evaluation for response every 12 weeks, +/- 14 days. Refer to Section 8.3.3.

Response and progression will be evaluated in this study using the international criteria proposed by the revised Response Evaluation Criteria in Solid Tumors (RECIST) guideline (version 1.1).⁴⁸ Changes in the largest diameter (unidimensional measurement) of the tumor lesions and the shortest diameter in the case of malignant lymph nodes are used.

The objective malignant disease evaluation will determine the subject's response, except when the subject presents with symptomatic deterioration ("clinical progression"). Patients with a global deterioration of health status requiring discontinuation of treatment without objective evidence of disease progression at that time should be classified as having *symptomatic deterioration*.

6.1 Malignant Disease Evaluation

To assess objective response, it is necessary to estimate the overall tumor burden at baseline to which subsequent measurements will be compared. Measurable disease is defined by the presence of at least one measurable lesion.

All measurements should be recorded in metric notation by use of a ruler or calipers. The same method of assessment and the same technique should be used to characterize each identified lesion at baseline and during follow-up. All baseline evaluations should be performed as closely as possible to the beginning of treatment and never more than 28 days before registration.

Refer to Section 8.1 Screening/Pre-treatment Evaluations.

The term unevaluable in reference to measurability will not be used because it does not provide additional meaning or accuracy.

At baseline, the primary tumor and pathologic neck lymph nodes will be characterized as either measurable or non-measurable.

6.1.1 Measurable Disease

Primary and/or Metastatic HNSCC Tumors (non-Lymph node):

• Lesions that can be accurately measured in at least one dimension (longest diameter to be recorded) as ≥ 20 mm (2.0 cm) with conventional techniques or as ≥ 10 mm (1.0 cm) with spiral CT scan.

Lymph Nodes:

- Lymph nodes are considered pathologic and measurable if short axis ≥ 15 mm.
- Lymph nodes are considered pathologic but non-measurable if short axis ≥ 10 mm but <
 15 mm.
- Lymph nodes are considered non-pathologic and non-measurable if short axis < 10 mm.

6.1.2 Non-measurable disease

All other lesions, including small lesions [longest diameter < 20 mm (2.0 cm) with conventional techniques or < 10 mm (1.0 cm) with spiral CT scan] are truly non-measurable lesions.

Lesions considered to be truly non-measurable include the following: bone lesions, leptomeningeal disease, ascites, pleural/pericardial effusion, inflammatory breast disease, lymphangitis cutis/pulmonis, abdominal masses that are not confirmed and followed by imaging techniques, and cystic lesions.

6.1.3 Target Lesions

Measurable lesions up to a maximum of 2 lesions per organ and 5 lesions in total, representative of all involved organs, should be identified as target lesions and recorded and measured at baseline. Target lesions should be selected on the basis of their size (lesions with the longest diameter), be representative of all involved organs, but in addition should be those that lend themselves to reproducible repeated measurements. It may be the case that, on occasion, the largest lesion does not lend itself to reproducible measurement in which circumstance the next largest lesion which can be measured reproducibly should be selected. A sum of the diameters (longest for non-nodal lesions, short axis for nodal lesions) for all target lesions will be calculated and reported as the baseline sum diameters. If lymph nodes are to be included in the

sum, then only the short axis is added into the sum. The baseline sum diameters will be used as reference to further characterize any objective tumor regression in the measurable dimension of the disease.

6.1.4 Non-target Lesions

All other lesions (or sites of disease) including any measurable lesions over and above the 5 target lesions should be identified as non-target lesions and should also be recorded at baseline. Measurements of these lesions are not required, but the presence, absence, or in rare cases unequivocal progression of each should be noted throughout follow-up.

6.2 Response Criteria

6.2.1 Evaluation of Target Lesions

Complete Response (CR) of Target Lesions

Disappearance of all target lesions. Any pathological lymph nodes (whether target or non-target) must have reduction in short axis to <10 mm.

Partial Response (PR) of Target Lesions

At least a 30% decrease in the sum of target lesion diameters (longest diameter of non-nodal lesions; short axis diameter of the target lymph nodes), taking as reference the *baseline sum diameter*.

Stable Disease (SD) of Target Lesions

Neither sufficient shrinkage to qualify for PR nor sufficient increase to qualify for PD, taking as reference the smallest sum diameters while on study.

Progressive Disease (PD) of Target Lesions

At least a 20% increase in the sum of target lesion diameters (longest diameter of non-nodal lesions; short axis diameter of the target lymph nodes), taking as reference the *smallest sum diameter* recorded since the baseline sum diameter measurements. In addition to the relative increase of 20%, the sum must also demonstrate an absolute increase of at least 5 mm. Note: the appearance of one or more new lesions is also considered progressions.

6.2.2 Evaluation of Non-target Lesions

All other lesions or sites of disease. Measurements of these lesions are not required, but the presence, absence, stable, or progression of each must be noted throughout follow-up.

Complete Response (CR) of Non-target Lesions

The disappearance of all nontarget lesions.

Partial Response/Stable Disease (SD) of Non-target Lesions

Confidential

Page 41 of 76 v10, 05/23/2023

The persistence of one or more nontarget lesion(s).

Progressive Disease (PD) of Non-target Lesions

The appearance of one or more new lesions and/or unequivocal progression of existing nontarget lesions. Unequivocal progression should not normally trump target lesion status. It must be representative of overall disease status change, not a single lesion increase.

Although a clear progression of "non-target" lesions only is exceptional, the opinion of the treating physician should prevail in such circumstances, and the progression status should be confirmed at a later time by the review panel (or Principal Investigator).

Evaluation of Patient's Best Overall Response

The best overall response is the best response recorded from registration until disease progression/recurrence, taking as reference for progressive disease the smallest measurements recorded since registration. Table 7 below provides overall responses for all possible combinations of tumor responses in target and nontarget lesions, with or without new lesions.

To be assigned a status of stable disease, measurements must have met the stable disease criteria at least once after study entry at a minimum interval of eight weeks (+/- 1 week).

| Target | Non-Target Lesions | New | Overall | Best Overall F |
|---------|--------------------|---------|----------|----------------|
| Lesions | | Lesions | Response | when Confirr |

Table 7: Evaluation for Patients with Measurable Disease (i.e., Target Disease)

| Target Lesions | Non-Target Lesions | New Lesions | Overall Response | Best Overall Response when Confirmation is Required* |
|-------------------|-----------------------------|----------------|---------------------|--|
| CR | CR | No | CR | ≥4 wks. Confirmation** |
| CR | Non-CR/Non-PD | No | PR | |
| CR | Not evaluated | No | PR | >4 wks. Confirmation** |
| PR | Non-CR/Non-PD/not evaluated | No | PR | |
| SD | Non-CR/Non-PD/not evaluated | No | SD | Documented at least once >4 wks. from baseline** |
| PD | Any | Yes or No | PD | |
| Any | PD*** | Yes or No | PD | No prior SD, PR or CR |
| Any | Any | Yes | PD | |

^{*} See RECIST 1.1 manuscript for further details on what is evidence of a new lesion.

Note: Patients with a global deterioration of health status requiring discontinuation of treatment without objective evidence of disease progression at that time should be reported as "symptomatic

^{**} Only for non-randomized trials with response as primary endpoint.

^{***} In exceptional circumstances, unequivocal progression in non-target lesions may be accepted as disease progression.

deterioration." Every effort should be made to document the objective progression even after discontinuation of treatment.

CR = complete response; PR = partial response; SD = stable disease; PD = progressive disease

First Documentation of Response

The time between initiation of therapy and first documentation of PR or CR.

Confirmation of Response

To be assigned a status of complete or partial response, changes in tumor measurements must be confirmed by repeat assessments performed no less than four weeks after the criteria for response are first met.

Duration of Response

Duration of overall response - the period measured from the time that measurement criteria are met for complete or partial response (whichever status is recorded first) until the first date that recurrent or progressive disease is objectively documented, taking as reference the smallest measurements recorded since treatment started.

Duration of Overall Complete Response

The period measured from the time measurement criteria are met for complete response until the first date that recurrent disease is objectively documented.

Duration of Stable Disease

A measurement from registration until the criteria for disease progression is met, taking as reference the smallest measurements recorded since registration. To be assigned a status of stable disease, measurements must have met the stable disease criteria at least once after study entry at a minimum interval of eight weeks (+/- 1 week).

Survival

Survival will be measured from the date of entry on study.

Time to Progression and Progression-free survival

This interval will be measured from the date of entry on the study to the appearance of new metastatic lesions or objective tumor progression.

Progression-free survival (PFS) will be calculated from treatment initiation to disease progression or death from any cause.

6.3 Methods of Measurement

Disease assessment is performed per standard of care.

All measurements should be taken and recorded in metric notation using a ruler or calipers. All baseline evaluations should be performed as closely as possible to the beginning of treatment and never more than 28 days before registration.

The same method of assessment and the same technique should be used to characterize each identified and reported lesion at baseline and during follow-up. Imaging-based evaluation is preferred to evaluation by clinical examination unless the lesion(s) being followed cannot be imaged but are assessable by clinical exam and measureable by ruler or caliper (clinical lesions).

Diagnostic CT scan is the preferred modality.

MRI may be substituted per investigator judgment (e.g., MRI of the neck with contrast, in cases where patient has an iodinated contrast allergy despite premedication).

PET/CT may only be used for tumor measurements if the CT component is of diagnostic quality. PET/CT where CT is performed only for attenuation correction is not of sufficient quality for RECIST measurements.

Clinical lesions Clinical lesions will only be considered measurable when they are superficial (e.g., skin nodules and palpable lymph nodes) and ≥10 mm diameter as assessed using a ruler or calipers (e.g., skin nodules). In the case of skin lesions, documentation by color photography, including a ruler to estimate the size of the lesion, is recommended.

Conventional CT and MRI This guideline has defined measurability of lesions on CT scan based on the assumption that CT slice thickness is 5 mm or less. If CT scans have slice thickness greater than 5 mm, the minimum size for a measurable lesion should be twice the slice thickness. MRI is also acceptable in certain situations (e.g. for body scans).

Use of MRI remains a complex issue. MRI has excellent contrast, spatial, and temporal resolution; however, there are many image acquisition variables involved in MRI, which greatly impact image quality, lesion conspicuity, and measurement. Furthermore, the availability of MRI is variable globally. As with CT, if an MRI is performed, the technical specifications of the scanning sequences used should be optimized for the evaluation of the type and site of disease. Furthermore, as with CT, the modality used at follow-up should be the same as was used at baseline and the lesions should be measured/assessed on the same pulse sequence. It is beyond the scope of the RECIST guidelines to prescribe specific MRI pulse sequence parameters for all scanners, body parts, and diseases. Ideally, the same type of scanner should be used and the image acquisition protocol should be followed as closely as possible to prior scans. Body scans

should be performed with breath-hold scanning techniques, if possible.

PET-CT At present, the low dose or attenuation correction CT portion of a combined PET-CT is not always of optimal diagnostic CT quality for use with RECIST measurements. However, if the site can document that the CT performed as part of a PET-CT is of identical diagnostic quality to a diagnostic CT (with IV and oral contrast), then the CT portion of the PET-CT can be used for RECIST measurements and can be used interchangeably with conventional CT in accurately measuring cancer lesions over time. Note, however, that the PET portion of the CT introduces additional data which may bias an investigator if it is not routinely or serially performed.

Ultrasound Ultrasound is not useful in assessment of lesion size and should not be used as a method of measurement. Ultrasound examinations cannot be reproduced in their entirety for independent review at a later date and, because they are operator dependent, it cannot be guaranteed that the same technique and measurements will be taken from one assessment to the next. If new lesions are identified by ultrasound in the course of the study, confirmation by CT or MRI is advised. If there is concern about radiation exposure at CT, MRI may be used instead of CT in selected instances.

Endoscopy, Laparoscopy The utilization of these techniques for objective tumor evaluation is not advised. However, such techniques may be useful to confirm complete pathological response when biopsies are obtained or to determine relapse in trials where recurrence following complete response (CR) or surgical resection is an endpoint.

Cytology, Histology These techniques can be used to differentiate between partial responses (PR) and complete responses (CR) in rare cases (e.g., residual lesions in tumor types, such as germ cell tumors, where known residual benign tumors can remain).

The cytological confirmation of the neoplastic origin of any effusion that appears or worsens during treatment when the measurable tumor has met criteria for response or stable disease is mandatory to differentiate between response or stable disease (an effusion may be a side effect of the treatment) and progressive disease.

FDG-PET While FDG-PET response assessments need additional study, it is sometimes reasonable to incorporate the use of FDG-PET scanning to complement CT scanning in assessment of progression (particularly possible 'new' disease). New lesions on the basis of FDG-PET imaging can be identified according to the following algorithm:

• Negative FDG-PET at baseline, with a positive FDG-PET at follow-up is a sign of PD based on a new lesion.

- No FDG-PET at baseline and a positive FDG-PET at follow-up: If the positive FDG-PET at follow-up corresponds to a new site of disease confirmed by CT, this is PD. If the positive FDG-PET at follow-up is not confirmed as a new site of disease on CT, additional follow-up CT scans are needed to determine if there is truly progression occurring at that site (if so, the date of PD will be the date of the initial abnormal FDG-PET scan). If the positive FDG-PET at follow-up corresponds to a pre-existing site of disease on CT that is not progressing on the basis of the anatomic images, this is not PD.
- FDG-PET may be used to upgrade a response to a CR in a manner similar to a biopsy in cases where a residual radiographic abnormality is thought to represent fibrosis or scarring. The use of FDG-PET in this circumstance should be prospectively described in the protocol and supported by disease-specific medical literature for the indication. However, it must be acknowledged that both approaches may lead to false positive CR due to limitations of FDG-PET and biopsy resolution/sensitivity.

Note: A 'positive' FDG-PET scan lesion means one which is FDG avid with an uptake greater than twice that of the surrounding tissue on the attenuation corrected image.

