 - Disease persistence or recurrence within 6 months of completing definitive radiotherapy for locally advanced disease, where platinum chemotherapy was administered as a component of induction and/or concurrent systemic treatment.
 - Disease progression during, or within 6 months, of treatment with platinum chemotherapy (e.g., carboplatin or cisplatin) in the recurrent and/or metastatic setting.

 The patient is not an acceptable candidate for platinum chemotherapy due to medical comorbidities, in the judgment of the local investigator.

Note: Prior platinum exposure may have occurred in any line of therapy (first line, second line, etc.) and is not required to be the most recent therapy received.

 Patients must have prior exposure to an anti-PD1 or anti-PDL1 mAb, if eligible for immunotherapy in the judgment of the local investigator.

Note: Prior exposure to investigational immunotherapies, including anti-CTLA4, anti-OX40, anti-CD40, anti-CD27, anti-TNFR antibodies or other investigational immunotherapies, is acceptable.

- Patients must have Eastern Cooperative Oncology Group (ECOG) Performance Status 0-1 at time of informed consent (see Appendix B).
- Patients must be age ≥ 18 years.
- Patients must consent to a research biopsy of tumor tissue at baseline, for conduct of
 correlative studies. In cases where a fresh biopsy is not feasible (i.e., if an accessible
 tumor site cannot be biopsied with acceptable clinical risk), archival tissue may be
 submitted instead, after discussion with and approval by the Sponsor-Investigator.
- Patients must have measurable disease per RECIST criteria, version 1.1 (see Section 6) per scan within 28 days prior to registration.
- Patients must have adequate electrolytes, liver, renal, and hematology function as defined below within 28 days of registration:
 - o Absolute neutrophil count (ANC) ≥ 1500/mm³
 - Platelet count (PLT) \geq 75,000/mm³
 - o Creatinine clearance ≥ 30 mL/min per estimated by the Cockraft-Gault formula:
 - Calculated Creatinine Clearance = [(140-age) X (actual body weight in kg) X (0.85 if female)]/(72 X serum creatinine)
 - o Total bilirubin ≤ 1.5 times upper-limit of normal (ULN)
 - AST (aspartate aminotransferase) ≤ 3 times ULN
 - ALT (alanine aminotransferase) ≤ 3 times ULN
 - Magnesium ≥ 1.2 mg/dL or 0.5 mmol/L*
 - Corrected Calcium ≥ 8.0 mg/dL or 2.0 mmol/L*
 - Potassium ≥ 3.0 mmol/L*
 - Serum albumin \geq 25 g/L (\geq 2.5 g/dL)

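### Sections 6.1.1 and 6.3 give different size floors for a measurable palpable lymph node (15 mm short axis against 10 mm diameter), and at the lower floor a small node can meet CR before PR

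*Combined protocol and SAP*

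**What the plan says.** **Nodes, Section 6.1.1.** "Lymph nodes are considered pathologic and measurable if short axis ≥ 15 mm". The next line covers smaller nodes: "Lymph nodes are considered pathologic but non-measurable if short axis ≥ 10 mm but" below 15 mm. Neither line is limited to a method of measurement.

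**Clinical lesions, Section 6.3.** "Clinical lesions will only be considered measurable when they are superficial (e.g., skin nodules and palpable lymph nodes) and ≥10 mm diameter", as judged by ruler or calipers. The sentence names palpable nodes, gives no axis and does not refer to 6.1.1.

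**Non-nodal lesions, Section 6.1.1.** The floor is "≥ 20 mm (2.0 cm) with conventional techniques or as ≥ 10 mm (1.0 cm) with spiral CT scan". Section 6.1.2 puts anything smaller among the truly non-measurable lesions. Section 6.3, by contrast, ties CT measurability to slice thickness: slices of 5 mm or less are assumed, and for thicker slices the floor is twice the thickness.

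**Response, Section 6.2.1.** For CR, any pathological node "must have reduction in short axis to <10 mm". PR needs a fall of at least 30% from the baseline sum of target diameters.

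**Use of measurability.** Section 3.1 states: "Patients must have measurable disease per RECIST criteria, version 1.1", with a pointer to Section 6 and the qualifier that this is judged per scan. Section 6.3 adds: "Imaging-based evaluation is preferred to evaluation by clinical examination unless the lesion(s) being followed cannot be imaged".

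**The concern.** A 12 mm palpable neck node is non-measurable under 6.1.1 and meets the stated floor in 6.3. A site that follows 6.3 could enter it in the target sum, while a site that follows 6.1.1 would record it as non-target. Three things follow.

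- The nodal CR threshold is an absolute size and the PR threshold is a relative fall. The two are in the intended order only if target nodes start large enough. A 10 mm floor breaks that order.
- Target or non-target status decides which progression rule applies. Target lesions need a 20% and 5 mm increase in the sum; non-target lesions need unequivocal progression. Through this, a choice of lesion could touch a PFS date.
- Section 6.3 speaks only of diameter. Read as longest diameter, it could admit a node whose short axis is already below 10 mm, which 6.1.1 treats as non-pathologic.

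A separate ambiguity concerns the 20 mm floor. The term *conventional techniques* is never defined, so it is unclear whether it covers calipers, MRI or non-spiral CT.

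**Working it through.** The plan states no figure on this point that could be reproduced, so the check is direct arithmetic on its thresholds.

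**Inputs.** Nodal floors of 15 mm (6.1.1) and 10 mm (6.3); nodal CR below 10 mm and PR at a 30% fall (6.2.1); target PD at +20% and at least +5 mm (6.2.1); 33 eligible patients per arm (10.3).

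**Step 1: when does CR come before PR?** For a single target node with baseline short axis b, PR needs a follow-up value of at most 0.70 × b, and target CR needs a value below 10 mm. CR comes first when 0.70 × b < 10, that is, b < 10/0.70 = 14.29 mm.

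| Baseline (mm) | PR at or below (mm) | Target CR below (mm) | Fall if node reaches 9.9 mm |
|---|---|---|---|
| 10 | 7.0 | 10 | 1.0% |
| 11 | 7.7 | 10 | 10.0% |
| 12 | 8.4 | 10 | 17.5% |
| 13 | 9.1 | 10 | 23.8% |
| 14 | 9.8 | 10 | 29.3% |
| 15 | 10.5 | 10 | 34.0% |

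A 12 mm node at 9.5 mm has fallen by (12 − 9.5)/12 = 20.8%. That meets target CR but not PR. At 15 mm the order is as intended, and any fall to below 10 mm exceeds (15 − 10)/15 = 33.3%.

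**Step 2: more than one node.** The result extends to node-only target disease averaging under 14.29 mm per node. A 15 mm and a 12 mm node that both reach 9.9 mm give (27 − 19.8)/27 = 26.7%. Two 15 mm nodes give (30 − 19.8)/30 = 34.0%.

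**Step 3: effect on the response rate.** One reclassified patient moves the rate by 1/33 = 3.0 percentage points. As an illustration, 5/33 = 15.2% becomes 6/33 = 18.2%. The exact 95% interval for 5/33 is 5.1% to 31.9%, so one case is small against the sampling error.

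**Step 4: progression.** As a sole target, a 12 mm node needs the larger of 12 × 1.20 = 14.4 mm and 12 + 5 = 17 mm, so 17 mm, for PD. As a non-target lesion it has no numeric threshold.

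**Step 5: the 20 mm floor.** The slice-thickness rule in 6.3 gives 2 × 10 = 20 mm for 10 mm slices, which agrees with 6.1.1. For thin-slice non-spiral CT or MRI, 6.1.1 may imply 20 mm, while 6.3 states no such floor. For skin nodules, the figures conflict (20 against 10 mm) only if calipers count as a conventional technique.

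**The case against.** The strongest defence is that the caliper route is hardly open. Section 3.1 judges measurable disease per scan, so on the literal text a lesion measured only by caliper qualifies nobody, and a node on CT falls under the 15 mm rule. Section 6.3 prefers imaging, and Section 8.3.2 and the study calendar specify CT or MRI. This stands. A reader might infer from the two floors that the same patient is eligible at one site and ineligible at another. For caliper-only lesions the documents do not support that.

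The second defence is that 6.3 only adds a condition to 6.1.1. The wording allows this, but the 10 mm figure would then have no effect on palpable nodes, which 6.3 names as an example. The text does not state this reading, so the conflict remains.

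The third defence is that a false CR has further hurdles. Overall CR also needs clearance of non-target lesions, all pathological nodes below 10 mm and no new lesions. The response definitions that follow Table 7 require confirmation after at least four weeks. This largely stands: a single measurement error would not suffice. Two limits apply. A footnote to Table 7 confines its own confirmation column to non-randomized trials with response as primary endpoint. And confirmation does not stop a node that stays at 9.5 mm.

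Finally, the skin-nodule conflict is conditional. *Conventional* is applied in 6.3 to CT and MRI, and a nodule measured on spiral CT has a 10 mm floor in both sections.

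**Conclusion.** The nodal inconsistency is real and in the current text. The CR-before-PR result is exact, but it applies only if a site takes caliper-measured nodes averaging under 14.29 mm as the whole of the target disease. Each such CR would be worth 3.0 percentage points of the secondary response rate in a 33-patient arm. An effect on PFS is possible only through target or non-target status, and its size cannot be worked out from the documents. They give no count of patients with such nodes.

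The skin-nodule, MRI and non-spiral CT floors are an ambiguity that rests on one undefined term, not an established contradiction. For MRI or non-spiral CT that ambiguity could reach eligibility, because these are scans. It would do so only for a patient with no other measurable lesion.

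The sections should be aligned because 6.3 as written permits a wrong response call and the correction is nearly free. The point does not threaten the trial's main conclusion.

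**What to change.** - In Section 6.3, remove palpable lymph nodes from the 10 mm sentence and state that nodes follow 6.1.1 (short axis of at least 15 mm) by any method.
- In Sections 6.1.1 and 6.1.2, define or delete the 20 mm floor for conventional techniques, so that it agrees with the caliper and slice-thickness rules in 6.3.

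Section 5.1 ends ficlatuzumab dosing by March 31, 2021, so the same rule should also be fixed for the response analysis. A list of patients whose target lesions include a node under 15 mm or a caliper-measured lesion would show whether anyone is affected.

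The cost is a few lines of wording and one listing. The downside is that palpable nodes of 10 mm to under 15 mm can only be non-target lesions, which 6.1.1 already implies by calling them non-measurable.
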